4.5 Study Duration

Patient enrollment in Cohort 1 occurred over 3 years and 9 months. Enrollment in Cohort 2 is expected to occur over approximately 2 years. Total study duration is expected to be approximately 6 years.

5 ELIGIBILITY CRITERIA

This eligibility checklist is used to determine patient eligibility and filed with the enrolling investigators signature in the patient research chart.

Patient No. _____

Patient's Initials: (L,F,M) _____

5.1 Inclusion Criteria

Yes/No (Response of "no" = patient ineligible)

5.1.1 Histologically confirmed endometrial carcinoma: endometrioid type, serous, and clear cell to include tumors originating in the cervix, but are primarily located in the uterus, and for whom vaginal cuff brachytherapy is indicated. Carcinosarcoma and other sarcomas are permitted. FIGO stage I and stage II, with one of the following combinations of stage and grade (Appendix A and C):

Stage IA, grade 1 with LVSI, 2, 3

Stage IB, grades 1-3

Stage II, grades 1-3

Stage IIIA, grades 1-3, not receiving EBRT as part of adjuvant therapy.

5.1.2 Patients post hysterectomy and free from residual disease.

5.1.3 WHO/ECOG-performance status 0-2 (Appendix B).

5.1.4 Able to provide informed consent and willing to sign an approved consent form that conforms to federal and institutional guidelines.

5.1.5 Life expectancy of >2 years

5.2 Exclusion Criteria

Yes/No (Response of "yes" = patient ineligible)

5.2.1 Stages of endometrial carcinoma other than described in Inclusion 5.1.1.

5.2.2 Previous pelvic radiotherapy.

5.2.3 Concurrent malignancy requiring non-protocol anti-cancer treatment other than surgery.

I certify that this patient meets all inclusion and exclusion criteria for enrollment onto this study.

Investigator Signature

Date

Time

6 TREATMENT PLAN

6.1 Administration Schedule

Experimental arm: 11Gy will be prescribed to the surface with a minimal treatment length of 3 cm. Two fractions will be given, one week apart. For this instance a week apart indicates an intervening weekend between treatments. Ideally treatments would be 7 days apart. Inspection of the vaginal cuff is required to ensure there is no dehiscence. Dose should be optimized to the cylinder as seen in Figure 1, Appendix D, with dose normalized to 100% at the tip and at the midpoint of the active length. Dose at $\frac{1}{2}$ cm will be recorded also. In cases of fulminant LSVI, the entire vagina may be treated per physician discretion. In most scenarios, the maximal treatment length should not exceed 5 cm. CT simulation shall be performed.

Control arm: One of the following fractions schemes are permitted based on the decision of the treating physician:

- 7 Gy at $\frac{1}{2}$ cm x 3 fractions over no more than three weeks.
- 5-5.5 Gy at $\frac{1}{2}$ cm x 4 fractions over no more than three weeks.
- 6 Gy at the surface of the cylinder x 5 fractions over no more than three weeks.

6.1.1 Treatment Schedule

If chemotherapy is going to be used, the preferred sequence is vaginal cuff brachytherapy first; however, treatment sequence may be determined at the investigator's discretion.

It is recommended that patients begin cuff brachytherapy within 16 weeks of hysterectomy. In the event chemotherapy precedes brachytherapy, it is recommended that brachytherapy begins 2-6 weeks after completion of chemotherapy.

6.2 Prohibited Concomitant Medications/Treatments

Non-protocol anti-cancer therapy other than surgery for another malignancy.

6.3 Duration of Therapy

Patients in the experimental arm should have treatment completed within two weeks of the first fraction given. Patients in the control arm should have treatment completed within three weeks of the first fraction given.

7 TOXICITIES AND DOSEAGE MODIFICATION

This study will utilize the CTCAE (NCI Common Terminology Criteria for Adverse Events) Version 5.0 for adverse event and serious adverse event reporting.

7.1 Dose Modifications

No dose modifications will be permitted. If dose to bowel or bladder is felt to be unsafe, evacuation of bowel or bladder is recommended. Treatment may be delayed for up to 2 weeks longer due to medical necessity.

7.2 Supportive Care

All supportive measures consistent with optimal patient care will be given throughout the study.

7.2.1 Emotional Distress

Severe emotional distress will be defined by a QLQ-C30 total score of ≤ 71 . Study staff will notify the treating investigator of QLQ-C30 scores ≤ 71 , and the participant may be referred to additional institutional resources to address emotional distress, as needed.

7.2.2 Emotional Distress Due to Financial Toxicity

Severe emotional distress due to financial toxicity will be defined by a FACIT-Cost score of < 14 . Study staff will notify the treating investigator of FACIT-Cost scores < 14 , and the participant may be referred to institutional resources for billing and financial services, as needed.

8 STUDY CALENDAR

Examination	Screening ¹	Brachytherapy	Follow-up ⁶	Follow-up ⁶	Follow-up ⁶	Long term Follow-up ⁶
			1 month +/- 12 weeks	6 months +/- 12 weeks	12 months +/- 12 weeks	24 and 36 months +/- 12 weeks
Informed consent	X					
Medical history	X					
Eligibility criteria	X					
Vital signs	X		X	X	X	
Physical examination	X		X	X	X	
Pelvic exams	X		X	X	X	
WHO/ECOG performance status	X		X	X	X	
QLQ30 Questionnaire²		X	X	X	X	
EN24 Questionnaire²		X	X	X	X	
Collection of Cost Data⁴				X		
Collection of Distance Data⁷					X⁸	
Vaginal Cuff Brachytherapy³		X				
Adverse Event assessments		X	X	X	X	
Chart Review⁵						X
COHORT 2 Only						
COST-FACIT¹⁰			X			
Health Care Expense Survey¹¹		X	X			
NCI Diet History Questionnaire III (DHQ-3)⁹			X			
Physical Activity Questionnaire (ACT24)⁹			X			

1. All Pre-study/Screening procedures should be completed less than or equal to 12 weeks before study treatment.

2. Both the QLQ30 and EN24 questionnaires (appendix E and F) should be administered at baseline (prior to the first brachytherapy fraction) and at the 1 month, 6 month, and 12 month follow-up visits. See section 7.2.1 for guidance on participants experiencing severe emotional distress.
3. Subjects randomized to the control arm will undergo one of the three treatment options described in section 5 over no more than 3 weeks. Subjects randomized to the experimental arm will undergo the treatment described in section 5 over no more than 2 weeks. See Appendix D for treatment planning and dose reporting form.
4. Collection of cost data for analysis is described in section 9.2
5. The PI will continue to review patient medical charts at 24 and 36 months for disease reoccurrence at one of the following locations: vaginal, pelvic, or distant.
6. In person visits are preferred to allow for exams, so almost all visits will be done on site. If a patient is ill or cannot travel, questionnaires and history may be obtained via telemedicine. Missed exams will be considered deviations.
7. Patient's zip code and the location of the treatment facility will be collected and documented by the study staff.
8. If the information is not collected at the 12 month follow up visit, it will be collected at a subsequent time point or from patient's medical record.
9. Completion of the DHQ-3 and ACT24 is strongly encouraged, however, incompleteness will not result in a protocol deviation.
10. See section 7.2.2 for guidance on participants experiencing severe emotional distress due to financial toxicities.
11. It is recommended that the Healthcare Expense diary be given to the participant prior to radiation to accurately track expenses throughout treatment. The diary should be collected from the patient at a follow-up visit.

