1.1 Primary Objectives and Endpoint

1.1.1 Evaluate the non-inferiority of patient Health Related Quality of Life (HRQOL) using the Global Health Status from the QLQ-C30 in the 2 arms one month after treatment.

ENDPOINT: Scores determined from patient completed questionnaires will be compared between the two treatment arms one month after treatment completion.

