2 COHORT 2 (PILOT EXPANSION)

2.1 Primary Objective and Endpoint

2.1.1 The primary objective is to evaluate the frequency and severity of patient-reported financial toxicity in patients with early-stage endometrial cancer treated with vaginal cuff-brachytherapy (VCB) at one-month post-VCB.

ENDPOINT:

Patient-reported financial toxicity will be assessed through the Functional Assessment of Chronic Illness Therapy (FACIT)-Cost questionnaire, administered at 1 month post-brachytherapy

2.2 Exploratory Objectives:

2.2.1 Exploratory objectives will include evaluation of differences in patient-reported financial toxicity between cohorts, to assess any impact of treatment duration on outcomes.

ENDPOINT:

Mean scores for each individual measure will be reported and compared between the two arms enrolled in Cohort 2.

Using a COST < 26 as a cutoff for moderate financial distress, the proportion of patients experiencing moderate distress in each cohort will be reported and compared.

2.2.2 Exploratory objectives include evaluation of patient-reported diet and physical activity levels and quality of life in patients with early-stage endometrial cancer treated with vaginal cuff-brachytherapy (VCB) at one-month post-VCB.

ENDPOINT:

Patient-reported diet and physical activity levels will be assessed through the Health Care Expense Survey, NCI Diet History Questionnaire III (DHQ-3), and

Physical Activity Questionnaire (ACT24) administered at 1 month post-brachytherapy.

Quality-of-life will be assessed through to Evaluate responses to the QLQ30 Questionnaire, EN24 Questionnaire in the patient population.

Mean scores from FACIT-COST with be correlated with QLQ30 scores

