9 CRITERIA FOR EVALUATION AND ENDPOINT (COHORT 1)

9.1 Primary Objective

Evaluate the non-inferiority of patient HRQOL using the Global Health Status from the QLQ-C30 in the 2 arms one month after treatment.

All patients with a valid baseline and with a follow-up QOL questionnaire at one month post treatment will be included in the analysis. We are accounting for an approximate 5 per cent drop out rate. We anticipate a high compliance rate due to the short follow up interval for the primary endpoint. Patients without valid questionnaires will not be replaced. The baseline questionnaire is considered valid if filled out and dated by the patient before the starting date of trial treatment. Reasons for missing baseline and follow-up questionnaires will be assessed.

For the evaluation of the general quality of life the EORTC (European Organization for Research and Treatment of Cancer) Core questionnaire (QLQ-C30 version 3.0) will be used (Appendix E). The EORTC QLQ-C30 is a multidimensional, cancer-specific quality of life questionnaire developed by the EORTC Study Group on Quality of Life (QOL) for repeated assessments within clinical trials. It is developed in a cross- cultural setting and has been found valid and reliable for quality of life assessments in various cancer populations, irrespective of the specific diagnosis. Optional modules developed for specific diagnostic groups or specific treatment modalities can supplement it. The QLQ-C30 contains five functional scales (physical, cognitive, emotional, social and role functioning), a global health status/quality of life scale, three symptom scales (pain, fatigue and nausea/vomiting), and six single items assessing additional symptoms (dyspnoea, insomnia, loss of appetite, constipation, diarrhoea) and perceived financial impact. For the majority of the QLQ-C30 items a 4-point Likert-type response scale is used. Exceptions are the items for the global quality of life scale (where a 7-point scale is used). All subscale and individual item responses are linearly converted to 0 to 100 scales. A higher score for a functional and global quality of life scales represents a better level of functioning. For the symptom scales and items, a higher score reflects a higher level of symptoms and decreased quality of life.

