14.4.2 Serious Adverse Event (SAE)

Information about all serious adverse events will be collected and recorded.

A serious adverse event is an undesirable sign, symptom or medical condition which:

- Is fatal or life-threatening
- Results in persistent or significant disability/incapacity
- Is medically significant, i.e., defined as an event that jeopardizes the patient or may require medical or surgical intervention to prevent one of the outcomes listed above
- Causes congenital anomaly or birth defect
- Requires inpatient hospitalization or prolongation of existing hospitalization, unless hospitalization is for:
 - Routine treatment or monitoring of the studied indication, not associated with any deterioration in condition (procedures such as central line placements, paracentesis, pain control).
 - Elective or pre-planned treatment for a pre-existing condition that is unrelated to the indication under study and has not worsened since the start of study drug.

- Treatment on an emergency outpatient basis for an event not fulfilling any of the definitions of a SAE given above and not resulting in hospital admission.
- Social reasons and respite care in the absence of any deterioration in the patient's general condition.

SAE evaluation will begin after the first treatment and will continue until the first follow up visit, 28 days (+/- 14) after the completion of study treatment. If the patient is unable to attend the first follow up visit, the SAE reporting period will be extended to 56 days after the completion of study treatment.

Any death from any cause while a patient is receiving treatment on this protocol or up to 30 days after the last dose of protocol treatment, or any death which occurs more than 30 days after protocol treatment has ended but which is felt to be treatment related, must be reported.

Toxicities which fall within the definitions listed above must be reported as an SAE regardless if they are felt to be treatment related or not. Toxicities unrelated to treatment that do NOT fall within the definitions above, must simply be documented as AEs in the patient research chart.

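### The calendar lets the one-month visit that carries both primary endpoints fall as late as about day 114, and no section sets a narrower limit on the date of a one-month form

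*Combined protocol and SAP*

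**What the plan says.** Section 1.1.1 defines the Cohort 1 primary endpoint by questionnaire scores that "will be compared between the two treatment arms one month after treatment completion". Section 2.1.1 defines the Cohort 2 primary endpoint by the FACIT-COST questionnaire, "administered at 1 month post-brachytherapy".

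The calendar in Section 8 gives the first follow-up as "1 month +/- 12 weeks" and the next as "6 months +/- 12 weeks". QLQ-C30 and EN24 are collected at both visits. COST-FACIT is collected only at the first. The calendar does not say from which date it counts. Note 6 adds: "If a patient is ill or cannot travel, questionnaires and history may be obtained via telemedicine".

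Section 14.4.2 runs SAE evaluation "until the first follow up visit, 28 days (+/- 14) after the completion of study treatment". If that visit cannot be attended, "the SAE reporting period will be extended to 56 days after the completion of study treatment".

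On the analysis side, Section 9.1 says patients with a valid baseline and "a follow-up QOL questionnaire at one month post treatment will be included in the analysis". The only date rule for a form in that section concerns the baseline questionnaire. Sections 10.1.1 to 10.1.3 and 10.2.1 to 10.2.5 give no date range for a one-month form. Section 10.2.2 includes every treated Cohort 2 subject with at least one set of questionnaires.

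**The concern.** The Global Health Status items ask about the past week (Appendix E, items 29 and 30) and COST-FACIT about the past 7 days (Appendix K). A form therefore describes the week in which it was completed, not the visit label it carries. If a form completed nearly four months after treatment counts as the one-month form, the quantity estimated is no longer the one the endpoint names.

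In Cohort 1, if the shorter course caused a temporary drop in Global Health Status, late forms would record some patients after recovery and move the comparison towards non-inferiority. In Cohort 2 there is no margin or primary test, so the issue is interpretation. Each arm's mean COST could mix patients shortly after treatment with patients months out, yet Section 3.3.1 wants these values as a baseline for later trials.

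The calendar and Section 14.4.2 also give sites two different windows for one visit.

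**Working it through.** **Inputs.** 12 weeks = 84 days (Section 8). One month is taken as 28, 30 or 30.4 days. The anchor is completion of treatment, as in Sections 1.1.1 and 14.4.2; for the calendar this is an assumption.

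**Windows.**
- Calendar, one month, upper limit: 28 + 84 = day 112; 30 + 84 = day 114.
- Calendar, one month, lower limit: 28 - 84 = day -56; 30 - 84 = day -54. Courses last two to three weeks (Section 6.3), so this is before treatment starts.
- Calendar width: 2 x 84 = 168 days.
- Section 14.4.2: 28 - 14 = day 14 to 28 + 14 = day 42, a width of 28 days. The calendar is 168 / 28 = 6 times as wide.
- Six-month window opens: 180 - 84 = day 96, or with calendar months 182.6 - 84 = day 98.6.
- Overlap with the one-month window: 114 - 96 = 18 days, or 114.4 - 98.6 = about 16 days.
- Days 14 to 42 satisfy both sections. Days 57 to 114 (58 days) are in window under the calendar but later than the 56-day fallback in Section 14.4.2.

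**The plan's own figures.** With SD 22.2, margin 15, true difference 0 and one-sided alpha 0.025 (Section 10.1.6), the noncentral t power at 48 per arm is 90.6%, which reproduces the stated 90% for 96 evaluable. For Cohort 2 (Section 10.2.1), 2 x t(0.975; 39 df) x 12 / sqrt(40) = 7.68 points, against about 7.6 stated. Neither figure is affected by the window.

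**Illustration for Cohort 1, late forms only.** The documents support none of these assumptions: the true one-month difference is exactly -15; a share *f* of forms is completed after day 42; and a fraction *r* of the deficit has resolved in those patients, so late experimental-arm patients sit at -15 x (1 - r). Simulation: 48 per arm, SD 22.2, 200,000 runs. False non-inferiority (nominal 2.5%):

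| r | f = 10% | 20% | 30% | 40% |
|---|---|---|---|---|
| 1 (upper bound) | 5% | 9% | 16% | 25% |
| 0.5 | 3.7% | 5.1% | 7.0% | 9.6% |
| 0.25 | 3.0% | 3.6% | 4.3% | 5.1% |
| 0 | 2.5% | 2.5% | 2.6% | 2.4% |

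If equal shares of 10 to 40% each are early (deficit half as large again) and late (deficit halved), the rate stays at about 2.5%. If the true difference is 0, as Section 10.1.6 assumes, there is no deficit to dilute.

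**The case against.** Much can be said for the plan as written.

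- The calendar is itself a limit, so it would be wrong to say that the date of a one-month form is unlimited. What is missing is a narrower or analysis limit.
- Section 14.4.2 is written for SAE reporting, lies inside the calendar window and has its own fallback. A reader might infer that no visit can satisfy both sections; days 14 to 42 do. The two still differ on when the first follow-up visit is due.
- Calendar note 2 ties each QLQ-C30 and EN24 form to a named visit, so forms do carry a visit label. The overlap with the 6-month window bears on the repeated-measures analysis in Section 10.1.3, which is exploratory. It does not touch COST-FACIT.
- The window is symmetric, and early forms could offset late ones. This stands against any one-directional claim of bias.
- Section 4.2 says Cohort 1 is enrolled and analysed, and Cohort 2 reports preliminary means without a primary test. The inferential harm is therefore hypothetical.

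A reader might also infer that late forms were used and that the Cohort 1 comparison was tilted towards non-inferiority. The documents give no form dates, no recovery rate and no sign of a true deficit, so they do not support that.

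Finally, a reader might infer that the expense survey and diary contradict the calendar. Their periods (40 days in Appendix I, 6 to 10 weeks in Appendix J) both end inside the present window, and note 11 lets the diary be collected at a follow-up visit without naming which.

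None of this removes the core: the stated tolerance is far wider than an endpoint defined at one month implies, and Section 9.1 itself relies on a short follow-up interval.

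**Conclusion.** The point holds as a defect in the definition of endpoint timing. The visit that carries both primary endpoints may nominally fall anywhere up to about day 112 to 114, six times the width given for the same visit in Section 14.4.2, and nothing in the analysis sections narrows it. The day counts assume that the calendar runs from completion of treatment.

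The effect on either cohort's results cannot be known from the documents. The 5 to 25% in the first row of the table is the upper end of a late-forms-only illustration under an assumed transient deficit at the margin, and is not an estimate. The point should be fixed, mainly for Cohort 2, where a window can still be set in advance. It gives no ground for calling the Cohort 1 result invalid.

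**What to change.** **Both cohorts.** Reconcile the calendar with Section 14.4.2 and state the date from which visits are counted.

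**Cohort 2, prospectively.** Set a narrower window for the one-month questionnaires that lies after completion of treatment and does not overlap the 6-month window. Use the telemedicine route in note 6 to meet it. Record the completion date of every form. Keep all one-month forms in the main estimate, consistent with Section 10.2.2. Report days since treatment by arm and add an in-window sensitivity analysis.

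Check the chosen window against the Expense Survey, because a survey completed before day 40 cannot cover its 40-day period. With days 14 to 42, for example, 26 of the 29 days precede day 40. The diary needs no change on this account.

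**Cohort 1.** Keep the planned analysis as primary, report actual assessment times by arm, and add an in-window analysis labelled as sensitivity, with its lower power stated.

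**Cost.** Wording changes, and some Cohort 2 visits may become deviations. The main estimates lose no data; only the in-window analyses lose precision:

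| Forms outside window | Cohort 1 power (n per arm) | Cohort 2 CI width (n per arm) |
|---|---|---|
| 0% | 90.6% (48) | 7.68 (40) |
| 10% | 87.2% (43) | 8.12 (36) |
| 20% | 82.8% (38) | 8.65 (32) |
| 30% | 77.1% (33) | 9.31 (28) |
| 40% | 70.0% (28) | 10.13 (24) |

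Restriction by date may also select on illness or finances. If out-of-window patients differ by an assumed *D* COST points, the in-window mean differs from the all-forms mean by f x D. With D = 6 this is 0.2 x 6 = 1.2 points at 20% outside and 0.4 x 6 = 2.4 at 40%, against a full-sample half-width of 7.68 / 2 = 3.84. That is why the restricted set should stay a sensitivity analysis.

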9 CRITERIA FOR EVALUATION AND ENDPOINT (COHORT 1)

9.1 Primary Objective

Evaluate the non-inferiority of patient HRQOL using the Global Health Status from the QLQ-C30 in the 2 arms one month after treatment.

All patients with a valid baseline and with a follow-up QOL questionnaire at one month post treatment will be included in the analysis. We are accounting for an approximate 5 per cent drop out rate. We anticipate a high compliance rate due to the short follow up interval for the primary endpoint. Patients without valid questionnaires will not be replaced. The baseline questionnaire is considered valid if filled out and dated by the patient before the starting date of trial treatment. Reasons for missing baseline and follow-up questionnaires will be assessed.

For the evaluation of the general quality of life the EORTC (European Organization for Research and Treatment of Cancer) Core questionnaire (QLQ-C30 version 3.0) will be used (Appendix E). The EORTC QLQ-C30 is a multidimensional, cancer-specific quality of life questionnaire developed by the EORTC Study Group on Quality of Life (QOL) for repeated assessments within clinical trials. It is developed in a cross- cultural setting and has been found valid and reliable for quality of life assessments in various cancer populations, irrespective of the specific diagnosis. Optional modules developed for specific diagnostic groups or specific treatment modalities can supplement it. The QLQ-C30 contains five functional scales (physical, cognitive, emotional, social and role functioning), a global health status/quality of life scale, three symptom scales (pain, fatigue and nausea/vomiting), and six single items assessing additional symptoms (dyspnoea, insomnia, loss of appetite, constipation, diarrhoea) and perceived financial impact. For the majority of the QLQ-C30 items a 4-point Likert-type response scale is used. Exceptions are the items for the global quality of life scale (where a 7-point scale is used). All subscale and individual item responses are linearly converted to 0 to 100 scales. A higher score for a functional and global quality of life scales represents a better level of functioning. For the symptom scales and items, a higher score reflects a higher level of symptoms and decreased quality of life.

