10.1.1 Primary Objective

The primary objective is to evaluate the non-inferiority of patient Health Related Quality of Life (HRQOL) in the Experimental arm compared to the Control arms one month after treatment. The primary efficacy variable is the Global Health status from the EORTC QLQ-C30. The EORTC QLQ-C30 is a multidimensional, cancer-specific quality of life questionnaire developed by the EORTC Study Group on Quality of Life (QOL) for repeated assessments within clinical trials. All patients with valid non-missing baseline and one month follow up Global Health Status will be included in the analysis. See below for handling of missing items.

The primary hypothesis is that the Global Health Status is non-inferior in the Experimental Arm compared to the Control Arm. Let μ_E and μ_C be the mean Global Health status in the Experimental and Control Arms respectively. The null hypothesis (H_0) and alternative hypothesis (H_1) are

$$H_0: \mu_E - \mu_C \leq -15 \text{ and } H_1: \mu_E - \mu_C > -15$$

A two sample t test will be used for the primary analysis. As a sensitivity analysis we will use analysis of covariance with Global Health Status at one month post therapy as Gaussian response variable, treatment group as a fixed effect and baseline Global Health Status as a continuous adjustment variable.

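### Cohort 1: the primary t test does not use the baseline score, yet patients without a valid baseline are excluded from it, and section 9.1 defines validity more strictly than the calendar

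*Combined protocol and SAP*

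**What the plan says.** Section 9.1 (headed as Cohort 1) sets the analysis set: "All patients with a valid baseline and with a follow-up QOL questionnaire at one month post treatment will be included in the analysis". Section 10.1.1 repeats the double requirement: "All patients with valid non-missing baseline and one month follow up Global Health Status will be included in the analysis". Section 9.1 adds: "Patients without valid questionnaires will not be replaced".

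On validity, section 9.1 says: "The baseline questionnaire is considered valid if filled out and dated by the patient before the starting date of trial treatment". The study calendar (section 8) marks the QLQ-C30 and EN24 in the Brachytherapy column and leaves the Screening column blank. Footnote 2 says that the forms "should be administered at baseline (prior to the first brachytherapy fraction) and at the 1 month, 6 month, and 12 month follow-up visits".

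On the analysis, section 10.1.1 says: "A two sample t test will be used for the primary analysis". The hypotheses there concern the difference in mean Global Health Status, and section 1.1 fixes the time at one month after treatment. The baseline score enters the sensitivity ANCOVA, which has "baseline Global Health Status as a continuous adjustment variable", and the exploratory repeated-measures model in section 10.1.3.

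**The concern.** A patient who was randomised, treated and returned a one-month questionnaire has supplied everything the primary test needs. If her baseline form is missing or invalid, the plan still leaves her out. The exclusion depends on paperwork from before treatment and not on the outcome.

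The two timing rules make such an exclusion more likely. Section 9.1 works on the calendar date and footnote 2 on the order of form and fraction. They part company for a form completed on the day of fraction 1 but before it. The QLQ-C30 in Appendix E has a date field and no time field, so the form alone cannot show the order.

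At stake are the number of patients in the primary non-inferiority test and its reproducibility: two analysts who each follow the protocol could arrive at different primary analysis sets.

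**Working it through.** **1. Does the primary test need the baseline?**

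| Analysis | Section | Uses baseline? |
|---|---|---|
| Primary two-sample t test, one-month score | 10.1.1 | No |
| Sensitivity ANCOVA | 10.1.1 | Yes, as covariate |
| Exploratory repeated-measures model | 10.1.3 | Yes, as a time point |

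The requirement is needed for the second analysis and relevant to the third. It is not needed for the first.

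**2. Where do the timing rules differ?**

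| Baseline form completed | Footnote 2 | Section 9.1, read literally |
|---|---|---|
| On an earlier day | Meets | Meets |
| Day of fraction 1, before it | Meets | Fails |
| After fraction 1 | Fails | Fails |

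Only the middle row is in conflict.

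**3. Reproducing the plan's sample size.** Inputs from section 10.1.6: SD 22.2, margin 15, true difference 0, one-sided alpha 0.025, 1:1 allocation, 96 evaluable for 90% power, 108 randomised.

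- Normal approximation: n per arm = 2 × (1.960 + 1.282)² × 22.2² / 15² = 46.0, rounded up to 47, or 94 in total.
- Noncentral t with 48 per arm: SE = 22.2 × √(2/48) = 4.53; noncentrality = 15 / 4.53 = 3.31; 94 degrees of freedom; power 90.6%. With 47 per arm it is 89.99%, so 96 is the smallest equal-arm total that reaches 90%.
- Inflation for 10% dropout: 96 / 0.90 = 106.7, or 107, consistent with 108.

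The stated figures reproduce. The 108 leaves room for 108 − 96 = 12 non-evaluable patients for all reasons together.

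**4. Effect of voided baselines.** The documents do not give the share of otherwise evaluable patients whose baseline would be voided, so the shares below are assumptions. Evaluable N = 108 × (1 − dropout) × (1 − share voided). Power is from the noncentral t with N/2 per arm. Section 10.1.6 assumes about 10% dropout and section 9.1 about 5%, so both are shown.

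| Share voided | N, 10% dropout | Power | N, 5% dropout | Power |
|---|---|---|---|---|
| 0% | 97.2 | 90.9% | 102.6 | 92.4% |
| 5% | 92.3 | 89.5% | 97.5 | 91.0% |
| 10% | 87.5 | 87.8% | 92.3 | 89.5% |
| 25% | 72.9 | 81.2% | 77.0 | 83.3% |

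At whole numbers of patients, power is 89.4% for 92, 87.6% for 87 and 81.3% for 73.

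**The case against.** **Cohort 1 is finished.** Section 4.2 says that its enrolment and data analysis are complete, so planning power can no longer be saved, and rewriting the primary set now would be post hoc. This stands and shapes the remedy. It does not remove the need to say which rule produced the reported analysis set.

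**The rules are compatible.** A reader might infer that the calendar fixes the form on the day of fraction 1. It does not: the column covers the treatment period, footnote 2 sets only an upper limit, and section 11 allows up to 10 business days between registration and treatment. A form dated on an earlier day meets both rules. Section 9.1 also says that a form is valid if dated earlier, not only if. Nothing in the documents shows that any form was voided. All of this stands, and it limits the conflict to same-day forms. The needless baseline requirement remains even if there were none.

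**One common set is a defensible choice.** It keeps the t test and its ANCOVA on the same patients. That has some value, but the ANCOVA can state its own smaller set without shrinking the primary one.

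**The plan already has safeguards.** Section 9.1 says that reasons for missing forms will be assessed, section 10.1.2 allows optional multiple imputation as a sensitivity analysis, and the 12-patient allowance could absorb some invalid forms. These soften the loss. They do not put a patient with an observed outcome back into the primary test.

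**Bias.** A reader might suspect that the excluded patients differ by site or by distance from the centre. The documents give no evidence of this and no mechanism that would act differently between arms.

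**Cohort 2.** A reader might carry the problem forward because the calendar is shared. Section 10.2.2 sets a separate population rule, the primary endpoint is the one-month COST score, and section 10.2.4 plans no formal testing of the QLQ-C30. Neither the exclusion rule nor the power argument carries over.

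**Conclusion.** The point holds for Cohort 1. The plan requires a baseline that its primary test does not use, and section 9.1 and footnote 2 disagree about a form completed on the day of fraction 1 before treatment. Following the plan therefore drops randomised patients with an observed primary outcome whenever the baseline is missing or invalid.

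The size is unknown and may be small. Under the plan's own assumptions and 10% dropout, voiding 5%, 10% or 25% of the remaining patients gives about 89%, 88% or 81% power against 90.9% with none voided. Under the 5% dropout of section 9.1, voiding 5% still leaves 91.0%. A reader might infer a serious loss of power or a wrong sample size. The documents support neither: 96 and 108 reproduce, and no share of same-day forms is given. The firm conclusion is about the definition of the analysis set and the need to report how it was applied.

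**What to change.** In sections 9.1 and 10.1.1, define the set for the primary t test as all randomised patients with a valid one-month Global Health Status, and keep the baseline requirement for the ANCOVA only. In section 9.1, define a valid baseline as one completed before the first fraction, same day included, to match footnote 2.

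Because Cohort 1 has been analysed, its reported primary set should not be changed silently. The report should:

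- state which validity rule was applied;
- give, by arm, the number of patients with a one-month score who were excluded for baseline reasons;
- if there were any, present the t test with them restored as a labelled supplementary analysis.

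The cost is a few sentences in two sections, one count by arm and at most one re-run of the t test. The planned sample size does not change.
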